#### **4.4.2 Cautionary and Prohibited Therapy**

##### **4.4.2.1 Corticosteroids and Tumor Necrosis Factor–Alpha Inhibitors**

Systemic corticosteroids and tumor necrosis factor–alpha (TNF- $\alpha$ ) inhibitors may attenuate potential beneficial immunologic effects of treatment with atezolizumab. Therefore, in situations in which systemic corticosteroids or TNF- $\alpha$  inhibitors would be routinely administered, alternatives, including antihistamines, should be considered. If the alternatives are not feasible, systemic corticosteroids and TNF- $\alpha$  inhibitors may be administered at the discretion of the investigator.

Systemic corticosteroids are recommended, at the discretion of the investigator, for the treatment of specific adverse events when associated with atezolizumab therapy (refer to the guidelines in [Appendix 8](#) for details).

#### **4.4.2.2 Medications Given with Precaution due to Effects Related to Cytochrome P450 Enzymes**

Concomitant use of strong and moderate inhibitors of CYP3A (e.g., clarithromycin, itraconazole, ketoconazole, posaconazole, telithromycin, and voriconazole) should be used with caution during cobimetinib treatment because cobimetinib is a sensitive substrate of CYP3A and exposures will be increased in presence of these agents (approximately 7-fold increase in presence of itraconazole in healthy subjects).

Strong and moderate CYP3A inducers (e.g., rifampin, phenytoin, carbamazepine, and phenobarbital) should be avoided during cobimetinib treatment because they increase the metabolism of cobimetinib. Strong inducers of CYP3A4 should be avoided, or selection of an alternate concomitant medicinal product with no or minimal potential to induce CYP3A4 should be considered.

The above lists of cautionary medications are not necessarily comprehensive. The investigator should consult the prescribing information when determining whether a concomitant medication can be safely administered with study treatment. In addition, the investigator should contact the Medical Monitor if questions arise regarding medications not listed above.

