### 3.1.1.1 Cobimetinib and Atezolizumab Treatment Schedule

Cobimetinib will be administered orally at a starting dose of 60 mg QD starting on Day 1 through Day 21 followed by a 7-day rest of each 28-day cycle in all cohorts.

Atezolizumab will be administered by IV infusion at a fixed dose of 840 mg on Days 1 and 15 of each 28-day cycle. Patients in the biopsy cohort (Cohort 7) will begin dosing cobimetinib before atezolizumab and will receive 60 mg cobimetinib alone QD, starting on Day 1 through Day 14 for Cycle 1. Atezolizumab dosing (840 mg IV) will begin on Day 15 in Cycle 1 and will continue on Days 1 and 15 of every cycle thereafter. Both study drugs will be administered until unacceptable toxicity or loss of clinical benefit, as determined by the investigator, after an integrated assessment of radiographic and biochemical data, and clinical status (e.g., symptomatic deterioration such as pain secondary to disease). If one study drug is discontinued or temporarily withheld or dose reduced, the other study drug may be continued.

Because of the possibility of an initial increase in tumor burden caused by IC infiltration in the setting of a T-cell response (termed "pseudoprogression") with atezolizumab containing treatment, radiographic progression per RECIST v1.1 may not be indicative of true disease progression. In the absence of unacceptable toxicity, patients who meet criteria for disease progression per RECIST v1.1 while receiving cobimetinib and/or atezolizumab will be permitted to continue study treatment if they meet all of the following criteria:

- Evidence of clinical benefit, as determined by the investigator following a review of all available data
- Absence of symptoms and signs (including laboratory values, such as new or worsening hypercalcemia) indicating unequivocal progression of disease
- Absence of decline in Eastern Cooperative Oncology Group (ECOG) Performance Status that can be attributed to disease progression

- Absence of tumor progression at critical anatomical sites (e.g., leptomeningeal disease) that cannot be managed by protocol-allowed medical interventions
- Patient's written consent to acknowledge deferring other treatment options in favor of continuing study treatment at the time of initial disease progression

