**Table 4 Recommended Cobimetinib Dose Modifications**

Grade (NCI CTCAE v4.0)	Recommended Cobimetinib Dose
Grade 1 or Grade 2 (tolerable)	No dose reduction. Maintain cobimetinib at the same dose of 60 mg QD (3 tablets).
Grade 2 (intolerable) or Grade 3 or 4 (any)	
First appearance	Interrupt treatment until Grade $\leq$ 1, restart treatment at 40 mg QD (2 tablets).
Second appearance	Interrupt treatment until Grade $\leq$ 1, restart treatment at 20 mg QD (1 tablet).
Third appearance	Consider permanent discontinuation.

NCI CTCAE v4.0=National Cancer Institute Common Terminology Criteria for Adverse Events, Version 4.0; QD=once a day.

*Note: Cobimetinib dose re-escalation is permitted on a case-by-case basis after discussion with the Medical Monitor or  designee.*

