**Table 5 Guidelines for Management of Patients Who Experience Specific Adverse Events (Cobimetinib and Atezolizumab)**

Event	Action to Be Taken
General guidance for dose modifications and treatment delays and discontinuation	
 
• There will be no dose modifications for atezolizumab.
 
• If atezolizumab is withheld and corticosteroids are initiated for an atezolizumab-related toxicity, corticosteroids must be tapered over <math>\geq 1</math> month to <math>\leq 10</math> mg/day oral prednisone or equivalent before atezolizumab can be resumed.a, b The dose of cobimetinib can be reduced by 20 mg (1 dose level) up to 2 times (i.e., from 60 mg to 40 mg and then from 40 mg to 20 mg). If further dose reduction is indicated after two dose reductions, the patient must discontinue cobimetinib but may continue treatment with atezolizumab at the investigator's discretion.
 
• If atezolizumab is discontinued, treatment with cobimetinib may be continued at the investigator's discretion and after discussion with the Medical Monitor.
 
• If cobimetinib is withheld for <math>> 28</math> days because of toxicity, the patient should be discontinued from cobimetinib, unless resumption of treatment is approved by the Medical Monitor after discussion with the investigator.
 

IRRs, anaphylaxis, and hypersensitivity reaction	
 
• Guidelines for management of IRRs are provided in Appendix 8.
 
• For anaphylaxis precautions, see Appendix 7.
 
• For severe hypersensitivity reactions, permanently discontinue all study treatment.
 

IRR = infusion-related reaction.

a Atezolizumab may be withheld for a period of time beyond 12 weeks to allow for corticosteroids to be reduced to  $\leq 10$  mg/day oral prednisone or equivalent. The acceptable length of the extended period of time must be agreed upon by the investigator and the Medical Monitor.

b Resumption of atezolizumab may be considered in patients who are deriving benefit and have fully recovered from the immune-related event. Patients can be rechallenged with atezolizumab only after approval has been documented by both the investigator (or an appropriate delegate) and the Medical Monitor.

**Table 5 Guidelines for Management of Patients Who Experience Specific Adverse Events (Cobimetinib and Atezolizumab) (cont.)**

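### Section 4.4.2.2 permits strong CYP3A inhibitors with caution, despite a stated 7-fold rise in cobimetinib exposure with itraconazole that no dose level offsets, and gives no avoid-or-withhold rule

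*Combined protocol and SAP*

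**What the plan says.** Section 4.4.2.2 covers strong and moderate CYP3A inhibitors together. It names six examples, itraconazole among them, and asks for caution because cobimetinib "exposures will be increased in presence of these agents (approximately 7-fold increase in presence of itraconazole in healthy subjects". It adds: "The investigator should consult the prescribing information when determining whether a concomitant medication can be safely administered with study treatment". Questions about medications that the section does not list go to the Medical Monitor. CYP3A inducers, in the same section, are to be avoided. Strong inhibitor drugs do not appear among the prohibited therapies in Section 4.4.2.3.

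Table 5 sets the dose levels: "The dose of cobimetinib can be reduced by 20 mg (1 dose level) up to 2 times", that is 60, 40 and 20 mg. Section 4.3.1.1 supplies a 20-mg tablet only. Table 4 ties the levels to toxicity grade:

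- Grade 1 or tolerable Grade 2: "No dose reduction. Maintain cobimetinib at the same dose of 60 mg QD (3 tablets".
- First intolerable Grade 2 or any Grade 3 or 4 event: interrupt, then "restart treatment at 40 mg QD (2 tablets".
- Second such event: interrupt, then "restart treatment at 20 mg QD (1 tablet".

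Section 3.1.1.1 already allows the two drugs to be handled separately: "If one study drug is discontinued or temporarily withheld or dose reduced, the other study drug may be continued".

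**The concern.** The protocol quantifies a large interaction and then leaves the response to the investigator. The inhibitors named are antifungals and antibiotics, which a patient with advanced cancer may well need. The antibiotic exclusion in Section 4.1.2.2 applies only before study treatment starts.

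If a patient takes itraconazole with cobimetinib, the only dose adjustments in the protocol wait for an adverse event, and the first step is only to 40 mg. The cobimetinib risks in Section 5.1.1.1 include hemorrhage, serous retinopathy, left ventricular dysfunction and rhabdomyolysis. Sections 5.1.1.1.2 to 5.1.1.1.4 say that retinal, ejection-fraction and CPK changes can be symptom-free, so symptoms are a weak trigger. The documents do not say how far these risks rise with exposure.

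**Working it through.** **Inputs**

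- Fold increase with itraconazole: about 7, in healthy subjects (Section 4.4.2.2). This is a cited result without underlying data, so it cannot be reproduced here. The text does not say which exposure measure it refers to.
- Dose levels: 60, 40 and 20 mg once daily (Tables 4 and 5).
- Schedule: 21 dosing days and 7 days off per 28-day cycle (Section 4.3.2.1).

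**Assumptions:** exposure is proportional to dose, the factor is the same at each dose level, and the healthy-subject factor carries over to patients.

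**Step 1. Exposure relative to 60 mg alone = dose × fold / 60**

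| Dose | Dose × 7 | Relative exposure |
|---|---|---|
| 60 mg | 420 | 420/60 = 7.0 |
| 40 mg | 280 | 280/60 = 4.7 |
| 20 mg | 140 | 140/60 = 2.3 |

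**Step 2. Dose that would restore the 60-mg exposure = 60 / fold.** At 7-fold this is 60/7 = 8.6 mg, less than half of the only tablet supplied.

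**Step 3. Largest increase that each level offsets = 60 / dose.** For 40 mg it is 60/40 = 1.5-fold. For 20 mg it is 60/20 = 3-fold.

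**Step 4. Sensitivity at 20 mg (20 × fold / 60).** Folds of 2, 3, 5, 6, 7 and 8 give 0.67, 1.0, 1.67, 2.0, 2.33 and 2.67. Modest error around 7 does not change the conclusion. An inhibitor at or below 3-fold would be covered by 20 mg.

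**Step 5. What each existing control does**

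- Prescribing information (Section 4.4.2.2): consulted before co-administration. Its content is not in these documents, and the protocol states no resulting action.
- Medical Monitor contact (Section 4.4.2.2): for medications not listed. Itraconazole is listed.
- Toxicity assessment before each dose (Section 4.5), monthly CPK (Section 5.1.1.1.4), and serial ejection-fraction and eye examinations (Sections 4.5.8 and 4.5.9): these detect harm; they do not prevent the exposure.
- Ban on potent CYP3A4 inhibitors (Section 4.4.2.4): this stands under a food and herbal heading, with grapefruit juice as the example.

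None of these tells the investigator to avoid the inhibitor or to withhold cobimetinib.

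**Step 6. Cost of a hold.** With 21 days on and 7 off, a 14-day hold covers between 14 − 7 = 7 and 14 dosing days. A 21-day hold covers between 21 − 7 = 14 and 21.

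**Step 7. Number of patients affected.** The documents give no rate of inhibitor use. If 0%, 1% or 5% of about 250 patients took a strong inhibitor, that would be 0, 2.5 or 12.5 patients.

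**The case against.** The strongest reply is that the protocol does not ignore the interaction. It discloses the size, asks for caution, and directs the investigator to the prescribing information before the two drugs are combined. Cobimetinib is a marketed product with labelling and an Investigator's Brochure, and either may already say what to do. This stands in part. A reader might infer that a patient can take itraconazole with 60 mg cobimetinib in full compliance and that nothing is required until toxicity appears. The documents do not support that: Section 4.4.2.2 asks for a check beforehand, and Section 4.5 makes dosing conditional on acceptable clinical and laboratory findings. What remains is narrower. The protocol delegates the action instead of stating it, and the outcome of that delegation cannot be seen here.

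A second reply is that one figure is being generalised. This also stands. The documents quantify itraconazole only, and no factor is given for the other strong inhibitors or for moderate ones. A reader should not apply 7-fold to the whole class, and the point does not extend to moderate inhibitors.

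A third reply is that the remedy also relies on prescribing information. The roles differ. Under the proposed text the protocol fixes the action, and labelling supplies only the time for the inhibitor's effect to clear.

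**Conclusion.** The point holds in this limited form. For itraconazole, the one inhibitor with a stated factor, the lowest dose level leaves about 2.3 times the 60-mg exposure, and the starting dose gives about 7 times. This rests on dose proportionality and on the healthy-subject factor applying to patients. The dose levels respond to toxicity, and no control in the protocol amounts to an avoid-or-withhold rule. The present wording is therefore less protective than such a rule, and less strict than the wording for inducers in the same section.

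A reader might go on to infer a higher rate of serious adverse events or an effect on the efficacy endpoints. The documents support neither: they give no exposure-toxicity relation and no frequency of inhibitor use, and zero affected patients is possible. This is a safety instruction that should be made explicit, with no bearing on the planned statistical analyses.

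**What to change.** Add to Section 4.4.2.2 wording such as:

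*Strong CYP3A inhibitors are to be avoided while a patient is taking cobimetinib. If short-term use is unavoidable, cobimetinib is withheld until the inhibitor has been stopped and its effect has cleared according to its prescribing information; atezolizumab may continue. Cobimetinib restarts at the dose used before the hold. After a longer inhibitor course, or a hold of more than 28 days, resumption requires Medical Monitor approval.*

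Continuing atezolizumab alone is already allowed by Section 3.1.1.1. The 28-day limit extends the Table 5 rule, which applies when cobimetinib is withheld "because of toxicity, the patient should be discontinued from cobimetinib, unless resumption of treatment is approved by the Medical Monitor"; at present it does not cover holds for an interaction. The 7 days in Section 4.4.2.4 should not serve as a clearance time, because they are a pre-treatment restriction on food and herbal products.

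The cost is a wording change in the next amendment, with the approvals described in Section 9.6. For the patient, the cost is a different antimicrobial or missed cobimetinib doses: 7 to 14 of 21 in a cycle for a 14-day hold, and 14 to 21 for a 21-day hold.

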#### **4.4.2.3 Prohibited Therapy**

Use of the following concomitant therapies is prohibited as described below:

- Concomitant therapy intended for the treatment of cancer (including, but not limited to, chemotherapy, hormonal therapy, immunotherapy, radiotherapy, and herbal therapy), whether health authority–approved or experimental, is prohibited during study treatment until disease progression is documented and the patient has discontinued study treatment, with the exception of palliative radiotherapy and radiotherapy to the brain.
- Investigational therapy (other than protocol-mandated study treatment) is prohibited during study treatment.
- Treatment with live, attenuated vaccines (e.g., FluMist®) are prohibited within 4 weeks prior to initiation of study treatment, during treatment with atezolizumab, and for 5 months after the last dose of atezolizumab
- Systemic immunostimulatory agents (including, but not limited to, interferons and IL-2) are prohibited within 4 weeks or 5 half-lives of the drug, whichever is longer, prior to initiation of study treatment and during study treatment because these agents could potentially increase the risk for autoimmune conditions when given in combination with atezolizumab.

- Systemic immunosuppressive medications (including, but not limited to, prednisone, cyclophosphamide, azathioprine, methotrexate, thalidomide, and anti-TNF agents) are prohibited within 2 weeks of Cycle 1, Day 1 and during study treatment because these agents could potentially alter the efficacy and safety of atezolizumab.
- Systemic corticosteroids may not be administered as premedication to patients with an allergy to contrast agents used for tumor scans (see [Appendix 3](#) for information on tumor scans for patients with contrast allergies).

#### **4.4.2.4 Prohibited Food and Herbal Supplements**

Consumption of potent CYP3A4 enzyme inhibitors such as grapefruit juice and potent CYP3A4 enzyme inducers such as St. John's wort are prohibited starting 7 days prior to Day 1 of Cycle 1, during the study, and for 30 days after the last dose of study treatment.

### **4.5 STUDY ASSESSMENTS**

Refer to [Appendix 1](#) for the schedule of activities to be performed during the study. All activities must be performed and documented for each patient. Patients will be closely monitored for safety and tolerability throughout the study. Patients should be assessed for toxicity prior to each dose; dosing will occur only if the clinical assessment and local laboratory test values are acceptable.

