##### **4.5.6.2 Treatment (Local Laboratory)**

Samples for the following laboratory tests during treatment will be sent to the study site's local laboratory for analysis:

- Hematology: WBC count, RBC count, CBC, hemoglobin, hematocrit, count with differential (neutrophils, eosinophils, basophils, monocytes, and lymphocytes)

- Serum chemistry panel: glucose, BUN or urea, creatinine, sodium, potassium, magnesium, calcium, phosphorus, total bilirubin, ALT, AST, ALP, CPK, and others according to the schedule of activities (see [Appendix 1](#))
- Urine pregnancy test for women of childbearing potential
- Thyroid function test

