#### **5.3.1 Adverse Event Reporting Period**

Investigators will seek information on adverse events at each patient contact. All adverse events, whether reported by the patient or noted by study personnel, will be recorded in the patient's medical record and on the Adverse Event eCRF.

**After informed consent** has been obtained **but prior to initiation of study drug**, only serious adverse events caused by a protocol-mandated intervention (e.g., invasive procedures such as biopsies, discontinuation of medications) should be reported (see Section 5.4.2 for instructions for reporting serious adverse events).

**After initiation of study drug**, all adverse events will be reported until 30 days after the last dose of study drug.

Instructions for reporting adverse events that occur after the adverse event reporting period are provided in Section 5.6.

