## Appendix 1 Schedule of Activities (cont.)

Assessment/Procedure (Day Window)	Screening a	Cycle 1		Cycle 2		Cycle ≥3		Tx Discon b	ADA Visit c	Survival FU d
	Days -28 to -1	Day 1 (±3)	Day 15 (±3)	Day 1 (±3)	Day 15 (±3)	Day 1 (±3)	Day 15 (±3)	< 30 ( +3) Days after Last Dose	>90 Days ( -3) after Last Dose	Every 3 Months (±3 days)
ECHO or MUGA scan k	x			x		x k				
Optional WGS		x								
Tumor assessments l	x	Tumor assessments occur every 8 weeks.								
Serology m	x									
Thyroid function n	x	x		x		x n		x		
Ophthalmologic exam o	x			x		x o		x		
Pregnancy test p	x	x		x		x p		x		
Urinalysis q	x									
Concomitant medications r	x r	x r		x		x		x r		
Adverse events s	x s	x s	x	x	x	x	x	x s		x s
Tumor biopsy (Cohorts 1–6) t	x		x					x		
Tumor biopsy (Cohort 7 only)	x u		x v		x w			x x		
Biomarker blood samples y		x	x	x		x		x		
Biomarker PBMC samples y		x	x	x		x		x		
Biomarker plasma samples y		x				x		x		
Biomarker urine samples y, z		x				x		x		
Atezolizumab administration aa		x bb	x	x	x	x aa	x			
Dispense cobimetinib cc		x		x		x				
Survival and anti-cancer therapy follow-up										x d

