## Appendix 1 Schedule of Activities (cont.)

ADA=anti-drug antibody; Discon=discontinuation; ECHO=echocardiogram; ECOG=Eastern Cooperative Oncology Group; eCRF=electronic Case Report Form; FU=follow-up; HBcAb=hepatitis B core antibody; HBsAg=hepatitis B surface antigen; HBV=hepatitis B virus; HCV=hepatitis C virus; IRR=infusion-related reactions; LVEF=left ventricular ejection fraction; MUGA=multiple-gated acquisition; PBMC=peripheral blood mononuclear cell; PK=pharmacokinetic; RECIST v1.1=Response Evaluation Criteria in Solid Tumors, Version 1.1; T3=triiodothyronine; T4=thyroxine; Tx=treatment; WGS=whole genome sequencing.

Notes: All assessments should be performed within  $\pm 3$  days of the scheduled visit, unless otherwise specified. On treatment days, all assessments should be performed prior to dosing, unless otherwise specified. On treatment days, pre-infusion laboratory samples should be drawn 0–4 hours before the start of infusion, and post-infusion laboratory samples should be drawn 0–30 minutes after the end of infusion, unless otherwise specified.

Assessments shaded in gray should be performed as scheduled, but the associated data do not need to be recorded on the eCRF (except in the case of an adverse event).

- a Results of standard-of-care tests or examinations performed prior to obtaining informed consent and within 28 days prior to Day 1 may be used; such tests do not need to be repeated for screening.
- b Patients who discontinue study drug will return to the clinic for a treatment discontinuation visit *within 30 (+ 3) days after the last dose*. The visit at which response assessment shows progressive disease may be used as the study discontinuation visit.
- c Visit not specified by the protocol. Assessments should be performed as clinically indicated.
- d Required follow-up information will be collected via telephone calls and/or clinic visits every 3 months until death, loss to follow-up, or study termination by the Sponsor.
- e Informed consent must be documented before any study-specific screening procedure is performed and may be obtained up to 28 days before initiation of study treatment.

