- f Vital signs include respiratory rate, pulse rate, and systolic and diastolic blood pressure while the patient is in a seated position, and temperature. Record abnormalities observed at baseline on the General Medical History and Baseline Conditions eCRF. At subsequent visits, record new or worsened clinically significant abnormalities on the Adverse Event eCRF.
- g Vital signs will be recorded within 60 minutes prior to the infusion and otherwise as clinically indicated during or after the infusion.
- h Perform a limited, symptom-directed examination at specified timepoints or as clinically indicated. Record new or worsened clinically significant abnormalities on the Adverse Event eCRF. If physical examinations are assessed within 7 days of the Day 1, Cycle 1 visit, they do not have to be repeated on Day 1.
- i Hematology includes WBC count, RBC count, hemoglobin, hematocrit, platelet count, and differential count (neutrophils, eosinophils, basophils, monocytes, and lymphocytes).
- j Chemistry panel (serum) includes sodium, potassium, chloride, bicarbonate, glucose, BUN or urea, creatinine, total protein, magnesium, phosphorus, calcium, total and direct bilirubin, alkaline phosphatase, ALT, AST, CPK, and uric acid. Albumin will be assessed at screening only.

## Appendix 1

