### Schedule of Activities (cont.)

- 
- k Evaluation of LVEF by ECHO or MUGA scan must be performed at the following timepoints only for patients on cobimetinib: at screening; on Day 1 of Cycle 2 ( $\pm 1$  week); on Day 1 of Cycles 5, 8, 11, 14, 17, and every 3 treatment cycles thereafter (i.e., Cycles 20, 23, 26, etc.;  $\pm 2$  weeks for each); and at treatment discontinuation visit evaluation (unless evaluation performed within the previous 12 weeks showed no clinically significant findings and/or changes from baseline).
- l Tumor assessments will continue until disease progression per RECIST v1.1 or immune-modified RECIST unless patient continued treatment, loss of clinical benefit (for patients who continue treatment after disease progression according to RECIST v1.1 or immune-modified RECIST), withdrawal of consent, study termination by the Sponsor, or death, whichever occurs first. Patients who discontinue treatment for reasons other than disease progression (e.g. toxicity) will continue scheduled tumor assessments until disease progression, withdrawal of consent, study termination by Sponsor, or death, whichever occurs first.
- m All patients will be tested for HIV prior to the inclusion into the study and HIV-positive patients will be excluded from the study. HBV serology will include HBsAg, antibodies against HBsAg, and total HBcAb antibody (anti-HBcAb). HBV DNA should be obtained prior to enrollment if patient has a negative serology for HBsAg and a positive serology for anti-HBcAb. HCV serology will include HCV antibody (anti-HCV). HCV RNA should be obtained prior to enrollment if patient tests positive for anti-HCV.
- n Thyroid-function testing (thyroid-stimulating hormone, free T3 [or total T3 for sites where free T3 is not performed], and free T4) collected on Day 1 of Cycles 1–5, and every 2 cycles thereafter (i.e., Day 1 of Cycles 7, 9, 11, etc.) for patients on atezolizumab.

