- o Ophthalmologic examination must be performed at the following timepoints only for patients on cobimetinib: at screening; on Day 1 of Cycle 2 ( $\pm 1$  week); on Day 1 of Cycles 5, 8, and 11 (every 3 treatment cycles;  $\pm 2$  weeks); on Day 1 of Cycles 15, 19, and 23 (every 4 treatment cycles;  $\pm 2$  weeks); on Day 1 of Cycles 29, 35, 41, 47, and every 6 treatment cycles thereafter (i.e., Cycles 53, 59, 65, etc.;  $\pm 2$  weeks for each); and at treatment discontinuation visit evaluation (unless evaluation performed within the previous 12 weeks showed no clinically significant findings and/or changes from baseline).
- p All women of childbearing potential will have a serum pregnancy test at screening. Urine pregnancy tests will be performed on Day 1 ( $\pm 2$  weeks) of every cycle. If a urine pregnancy test is positive, it must be confirmed by a serum pregnancy test.
- q Includes dipstick (pH, specific gravity, glucose, protein, ketones, and blood) and microscopic examination (sediment, RBCs, WBCs, casts, crystals, epithelial cells, and bacteria).
- r Includes any medication (e.g., prescription drugs, over-the-counter drugs, herbal or homeopathic remedies, nutritional supplements) used by a patient from 7 days prior to initiation of study drug until 30 days after the last dose of study drug.
- s After informed consent has been obtained but prior to initiation of study drug, only serious adverse events caused by a protocol-mandated intervention should be reported. After initiation of study drug, all adverse events will be reported until 30 days after the last dose of study drug or initiation of new anti-cancer therapy, whichever occurs first. After this period, all deaths, regardless of cause, should be reported. After this period, the Sponsor should be notified if the investigator becomes aware of any serious adverse event that is believed to be related to prior study drug treatment (see Section 5.6). The investigator should follow each adverse event until the event has resolved to baseline grade or better, the event is assessed as stable by the investigator, the patient is lost to follow-up, or the patient withdraws consent. Every effort should be made to follow all serious adverse events or adverse events of special interest considered to be related to study drug or trial-related procedures until a final outcome can be reported.

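### Appendix 1 schedules no chemistry panel at treatment discontinuation, so patients who stop away from a Day 1 visit can leave without a scheduled check for silent liver, renal or CPK changes; a smaller gap precedes Cohort 7's first atezolizumab infusion

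*Combined protocol and SAP*

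**What the plan says.** **Discontinuation visit.** In Appendix 1 the chemistry row is marked at screening and at Day 1 of Cycles 1, 2 and 3 onward, and nowhere else. Hematology, thyroid function and the pregnancy test follow the same Day 1 pattern but are also marked in the Tx Discon column. Footnote j, attached to chemistry, lists the analytes, ending "alkaline phosphatase, ALT, AST, CPK, and uric acid. Albumin will be assessed at screening only", and names no further visit. Section 4.5.6.2 lists on-treatment tests "and others according to the schedule of activities", so it points back to the same table. The LVEF row is also blank at discontinuation, but there footnote k supplies the test: "and at treatment discontinuation visit evaluation". Chemistry has no equivalent.

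**Reporting window.** Section 5.3.1 says that after study drug starts, "all adverse events will be reported until 30 days after the last dose of study drug". Footnote s adds an earlier stop: "or initiation of new anti-cancer therapy, whichever occurs first". Section 5.4.2.2 applies the 30-day limit to adverse events of special interest. In Section 5.2.3 these include Hy's-law liver injury, hepatitis with AST or ALT above 10 × ULN, nephritis, and Grade 3 or higher CPK elevation.

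**Timing of the visit.** Footnote b asks for the discontinuation visit within 30 (+3) days of the last dose and adds: "The visit at which response assessment shows progressive disease may be used as the study discontinuation visit".

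**Cohort 7.** Sections 3.1.1.1 and 4.3.2.2 give cobimetinib alone on Days 1–14 and the first atezolizumab on Cycle 1 Day 15. The notes to Appendix 1 place treatment-day assessments before dosing unless otherwise specified. Neither hematology nor chemistry is marked at any Day 15. Section 4.5 says of each dose that "dosing will occur only if the clinical assessment and local laboratory test values are acceptable".

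**The concern.** The panel missing at exit is the one that carries ALT, AST, bilirubin, creatinine and CPK. Changes in these can be silent; Section 5.1.1.1.4 says most CPK elevations with cobimetinib were asymptomatic. Nor are they rare with this drug class. Section 1.2.6.2 reports increased CPK in 22.7% of 150 patients on this combination. Sections 5.1.1.1.4 and 5.1.1.2.1 report Grade 3 or higher CPK elevation in 11.3%, and Grade 3 or higher liver-test abnormalities in 20.5%, of patients on cobimetinib plus vemurafenib. Those are rates over treatment, the last two with a different partner drug, and not rates at exit. They show only that the panel has something to find. A patient can stop treatment with such a change present, reportable and unseen by any scheduled test.

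In Cohort 7 the issue is the basis for the first atezolizumab dose. Under Table 5, asymptomatic Grade 4 CPK elevation interrupts both drugs, AST/ALT above 3 × ULN with bilirubin above 2 × ULN withholds both, and AST/ALT above 10 × ULN stops both permanently. A value taken before any cobimetinib cannot show an effect of 14 days of it. Section 5.3.4 also asks for causality to be assessed for each drug separately.

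**Working it through.** **1. The cells (Appendix 1).**

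| Row | Screening | C1 D1 | C1 D15 | C2 D1 | C2 D15 | C≥3 D1 | C≥3 D15 | Tx Discon |
|---|---|---|---|---|---|---|---|---|
| Hematology | x | x | – | x | – | x | – | x |
| Chemistry | x | x | – | x | – | x | – | – |
| Thyroid | x | x | – | x | – | x | – | x |
| Pregnancy test | x | x | – | x | – | x | – | x |
| ECHO/MUGA | x | – | – | x | – | x | – | – (footnote k requires it) |

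Chemistry is the only laboratory row recurring on treatment that has no scheduled test at discontinuation.

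**2. Last scheduled chemistry to close of the adverse event window.** Take chemistry on Day 1 of a cycle and the last dose on Day d. Cobimetinib runs Days 1–21 and atezolizumab falls on Days 1 and 15, so d is 1 to 21. The window closes on Day d + 30.

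- No further Day 1 visit: (d + 30) − 1 = d + 29, so 30 days (d = 1) to 50 days (d = 21).
- Chemistry drawn at the next Day 1 visit (Day 29): (d + 30) − 29 = d + 1, so 2 to 22 days.
- If new anti-cancer therapy starts first, footnote s shortens both.

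**3. Who is exposed.** Scans are every 8 weeks = 56 days = two 28-day cycles. Counted from Cycle 1 Day 1 without delays, they fall on Days 57, 113 and 169, which are Day 1 of Cycles 3, 5 and 7. Chemistry is marked there, and footnote b lets a progression visit serve as the discontinuation visit. A patient stopping at such a scan therefore nominally has an exit panel. Section 3.1.1.2 keeps scans at 8-week intervals whatever the dose delays, so the alignment is lost once a cycle slips. The exposed group is those who stop away from a Day 1 visit with no later Day 1 draw: for toxicity, by choice, on symptomatic decline, or at an off-cycle scan. The documents do not size it.

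**4. After the fix.** With a draw v days after the last dose, the gap left is (d + 30) − (d + v) = 30 − v. For v from 0 to 30 that is 30 down to 0 days. One panel narrows the gap but need not close it.

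**5. Cohort 7.** The Day 1 draw is before the first cobimetinib dose.

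- Age of that value at the Day 15 infusion: 15 − 1 = 14 days, with 14 cobimetinib doses taken since. The ±3-day visit window gives 11 to 17 days; the ±7 days in footnote aa allows up to 21.
- Next scheduled hematology and chemistry: Cycle 2 Day 1 = Day 29, after 21 cobimetinib doses (Section 4.3.2.1), one atezolizumab infusion and 7 days off cobimetinib.
- An abnormal Day 15 value would place onset before atezolizumab. A normal Day 15 value followed by an abnormal Day 29 value would not separate the drugs, because cobimetinib continues on Days 15–21 alongside the first infusion.

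**The case against.** The strongest reply to the exit gap is that most of the relevant patients are already covered. Progression at an on-schedule scan coincides with a chemistry visit. Patients with a known laboratory toxicity are followed closely: LFTs at least weekly, or every 48–72 hours for severe elevations, and CPK at least weekly (Table 5); close creatinine monitoring for Grade 1 renal events (Appendix 8, Table 8); and follow-up to resolution or stability (Section 5.5.1). This stands, and it confines the gap to patients who stop off-cycle with a new silent abnormality. It does not remove the gap, because every one of these safeguards starts from a known event or a symptom.

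It can also be said that a blank cell is weak evidence of intent, since the LVEF cell is blank although the test is required. A clerical omission is plausible. But footnote k repairs the LVEF cell and nothing repairs chemistry, so a site that follows the plan exactly draws none.

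For Cohort 7, the reply is that Section 4.5 is itself the control and a site may draw fresh values under it, that the cohort exists to study tumor biology (Section 3.3.2.1), and that no planned analysis separates laboratory toxicity by drug. All of this stands and makes the Cohort 7 part secondary. What remains is that the dosing check has no scheduled post-cobimetinib value to work from. Section 4.5's sentence concerns dosing, so it has no bearing on the discontinuation visit.

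**Conclusion.** A cheap improvement. The main point is the missing discontinuation chemistry in all cohorts. For patients with no later Day 1 visit, the last scheduled panel comes 30 to 50 days before the adverse event window closes. The Cohort 7 point is secondary: about 12 patients, with values nominally 14 days old and taken before any cobimetinib. Both rest on the printed cells of Appendix 1, nominal visit days and no unscheduled draws.

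A reader might infer more than the documents support:

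- **That about 250 patients are exposed.** The full plan is 6 × 40 + 12 = 252, but that is an enrollment ceiling. Step 3 shows that many would have a coinciding panel.
- **That reported toxicity rates are biased.** Section 6.5 summarizes laboratory data over time and requires no discontinuation value. No effect on rates is shown.
- **That all Day 15 dosing is inadequately monitored.** Monthly CPK (Section 5.1.1.1.4) and four-weekly LFTs (Table 5) agree with the blank Day 15 cells. Cohorts 1–6 start atezolizumab on Day 1, with a pre-dose panel scheduled. Cohort 7 is singled out because its second drug starts on Day 15, not because its risk is shown to be higher.
- **That a Day 15 panel would separate the two drugs.** It does so in one direction only.

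**What to change.** In Appendix 1:

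- **Main change.** Mark chemistry (at least ALT, AST, bilirubin, creatinine and CPK) in the Tx Discon column for all cohorts, unless already drawn at a coinciding Day 1 visit.
- **Secondary change.** Mark hematology and chemistry at Cycle 1 Day 15 for Cohort 7 only, reviewed before the first atezolizumab infusion.

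Leave the four-weekly schedule for all other Day 15 doses, and all dosing thresholds, as they are.

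This is three cells and one cohort footnote, with no new visit. Biomarker blood is already scheduled at both timepoints, and Appendix 2 already takes serum before Cohort 7's Day 15 infusion and at the atezolizumab discontinuation visit. Planned enrollment is 6 × 20 + 12 = 132 to 6 × 40 + 12 = 252. The upper bound on added chemistry panels is thus 132 + 12 = 144 to 252 + 12 = 264, with 12 hematology panels. The true number is lower wherever discontinuation coincides with a Day 1 visit.

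The downside is in Cohort 7. Pre-infusion samples are drawn 0–4 hours before the infusion, so if local results are not back in that time the infusion waits or an earlier draw is needed. The mandatory biopsy between Days 10 and 14 would be a natural occasion for one.
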